			Visit 1 ^a	Visit 2 ^c	Visit 3 ^d	Visit 4	Visit 5	Visit 6	Visit 7	Visit 8 & 9	Visit 10	Visit 11	Visit 12 ^e	Visit 12.2 ^e	Visit 13	Visit 13.1 ^{kk}	Visit 13.2 ^e	Visit 14 ^b	Visit 14.2 ^e	Visit 15 ^e	Visit 16	Visit 17	Visit 18 ^f	Visit 19 ^b		
Visit Number/ Description	Visit 1 ^a	Visit 2 ^c	Screening	Baseline	Wee k 1, Day 1	Wee k 1, Day 2	Wee k 1, Day 4	Wee k 1, Day 6	Wee k 1, Day 7	Wee k 2, Day 8 & 9	Wee k 2, Day 10	Wee k 2, Day 14	Wee k 3	Wee k 4	Week 5	Week 6	We ek 7	We ek 9	We ek 11	We ek 13	We ek 18	We ek 35	We ek 47	We ek 52		
Visit Day	-90 to -30	-48 to -16	1	2	4	6	7	8 & 9	10	14	21	28	34	42	48	60	74	90	120	240	328	360				
Visit Window (± days)			0	0	0	0	0	0	0	1	1	1	1	3	3	3	3	3	7	7	14	7				
International normalized ratio (INR), Hepatitis A virus (anti-HAV) immunoglobulin M Hepatitis B surface antigen, Hepatitis C antibody ^l	X																							X		
Biomarker (creatinine kinase) ^l		X			X						X	X	X	X		X	X	X	X	X	X			X	X	
Banked biospecimens for biomarkers ^m	X																					X			X	
Banked biospecimens for genetics ⁿ																				X						
Urine Samples																										
Clinical safety (urinalysis) ^l	X		X	X	X						X			X			X			X			X		X	X ^g
Banked biospecimens for biomarkers ^m	X																						X		X	
Viral Vector Shedding ^z	X		X	X	X		X		X	X	X		X		X		X		X	X	X		X	X	X ^g	

Period	Screening	Baseline	Main Study Period (Year 1)																					Early Discontinuation Visit ^e	
			Visit 1 ^a	Visit 2 ^c	Visit 3 ^d	Visit 4	Visit 5	Visit 6	Visit 7	Visit 8 & 9	Visit 10	Visit 11	Visit 12 ^e	Visit 12.2 ^e	Visit 13	Visit 13.1 ^{kk}	Visit 13.2 ^e	Visit 14 ^b	Visit 14.2 ^e	Visit 15 ^c	Visit 16	Visit 17	Visit 18 ^f	Visit 19 ^b	
Visit Number/ Description	Screening	Baseline	Week 1, Day 1	Week 1, Day 2	Week 1, Day 4	Week 1, Day 6	Week 1, Day 7	Week 2, Day 8 & 9	Week 2, Day 10	Week 2, Day 14	Week 3	Week 4	Week 5	Week 6	Week 7	Week 9	Week 11	Week 13	Week 18	Week 35	Week 47	Week 52			
Visit Day	-90 to -30	-48 to -16	1	2	4	6	7	8 & 9	10	14	21	28	34	42	48	60	74	90	120	240	328	360			
Visit Window (± days)			0	0	0	0	0	0	0	1	1	1	1	3	3	3	3	7	7	14	7				
Saliva Samples																									
Viral Vector Shedding ^z	X		X	X	X		X		X	X	X		X		X		X		X	X	X		X	X ^g	
Tissue Samples																									
Muscle biopsy ^o		X																						X ^x	
Imaging Assessments																									
Echocardiogram ^p	X																							X	X ^g
Cardiac MRI ^{gg}		X ^{hh}																						X ^{hh}	
Functional Assessments																									

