FVC ^{q,y}	X																							X	X ^g
NSAA ^q	X	X														X			X	X			X	X	
Ankle range of motion	X	X														X			X	X			X	X	
Ambulatory status	X ^r															X			X	X			X	X	
Actigraphy ^s		X													X			X	X			X			
Clinical Outcome Assessments																									
Caregiver-completed																									
Modified PODCI – Pediatric Parent ^t		X																			X			X	X
EQ-5D-Y Proxy ^t		X																						X	X
EQ-5D-5L		X																						X	X
PGIS:CG ^t		X														X			X	X			X	X	

PFIZER CONFIDENTIAL

CT02-GSOP Clinical Protocol Template Phase 1 2 3 4 (04 September 2018)

Period	Screening	Baseline	Main Study Period (Year 1)																				Early Discontinuation Visit ^g		
			Visit 1 ^a	Visit 2 ^c	Visit 3 ^d	Visit 4	Visit 5	Visit 6	Visit 7	Visit 8 & 9	Visit 10	Visit 11	Visit 12 ^e	Visit 12.2 ^e	Visit 13	Visit 13.1 ^{kk}	Visit 13.2 ^e	Visit 14 ^b	Visit 14.2 ^e	Visit 15 ^c	Visit 16	Visit 17	Visit 18 ^f	Visit 19 ^b	
Visit Number/ Description	Visit 1 ^a	Screening	Visit 2 ^c	Screening	Baseline	Wee k 1, Day 1	Wee k 1, Day 2	Wee k 1, Day 4	Wee k 1, Day 6	Wee k 1, Day 7	Wee k 2, Day 8 & 9	Wee k 2, Day 10	Wee k 2, Day 14	Wee k 3	Wee k 4	Week 5	Week 6	We ek 7	We ek 9	Wee k 11	Wee k 13	Wee k 18	Wee k 35	Wee k 47	Wee k 52
Visit Day	-90 to -30	-48 to -16	1	2	4	6	7	8 & 9	10	14	21	28	34	42	48	60	74	90	120	240	328	360			
Visit Window (± days)			0	0	0	0	0	0	0	1	1	1	1	3	3	3	3	3	7	7	14	7			
Participant-completed																									
EQ-5D-Y ^t																								X X	
Clinical evaluator-completed																									
CGIS ^q																								X X	
Health economic questionnaires																									
HRU:CG																									
WPAI:DMD Caregiver																									
Interventions																									
Protocol-mandated glucocorticoid regimen ^u					X	X	→	→	→	→	→	→	→	→	→	→	→	→	→	→	→	X			
Background glucocorticoid regimen	X	X																				X	→	→	→
IP administration						X																			
Meningococcal vaccine	X	X																							
Ongoing monitoring																									
Concomitant medications	X	→	→	→	→	→	→	→	→	→	→	→	→	→	→	→	→	→	→	→	→	→	→	X	
Serious and nonserious adverse event monitoring	X	→	→	→	→	→	→	→	→	→	→	→	→	→	→	→	→	→	→	→	→	→	→	→	

Period	Screening	Baseline	Main Study Period (Year 1)																					Early Discontinuation Visit ^b

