5.3.1. Study and Year 1 IP Administration Eligibility

If, due to operational or administrative reasons (eg, enrollment pause due to regulatory or safety review, operational issues causing significant delays), the time between the Screening Visit (Visit 1) and the Day 1 Visit (Visit 3), is more than 90 days, participants will undergo an unplanned visit to repeat the following tests and procedures, as applicable, and will re-confirm all study/IP administration eligibility criteria:

- Full physical and neurological examination;
- Vital signs;
- Laboratory tests: clinical safety, chemistry and hepatic safety, cardiac troponin, INR, and hepatitis serology;
- NAb to AAV9, if the previous sample was collected more than 55 days before the day of IP administration (see [Section 6.1.1](#));

- Functional assessments: NSAA, ambulatory status;
- Echocardiogram and ECG;
- Medical history, concomitant medications, and background glucocorticoid regimen assessment.
- Weight: for participants who were already randomized but have not yet received IP, weight will be measured again following the process outlined in [Section 8.2.3](#). The site will update the weight in the IRT system, to allow re-calculation of the dose of IP if needed, once study eligibility is re-confirmed. Participants with an increase or decrease in body weight of more than 5% will have the dose of IP re-calculated.

If a participant has started or completed the Screening Visit (Visit 1), but was not yet randomized when the assessments are repeated, and he is found to be ineligible for study entry based on the results of repeated tests and procedures, he will be screen failed.

If a participant was already randomized, but had not yet received IP when the assessments are repeated, and he is found to be ineligible for study entry based on the results of the repeated tests and procedures, he will be withdrawn from the study.

For participants who completed the Baseline Visit (Visit 2) and were randomized, and who are re-confirmed to be eligible for study entry, a second unplanned visit will be scheduled to perform a NAb to AAV9 test if the Day 1 Visit (Visit 3) is expected to be more than 55 days after the collection of the previous sample.

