5.3.2. Year 2 IP Administration Eligibility

If, due to operational or administrative reasons (eg, enrollment pause due to regulatory or safety review, operational issues causing significant delays), a participant's Year 2 IP administration must be delayed, the Day 390 (Visit 20) and also subsequent visits will be delayed for that participant until the pause is lifted. Participants with delayed Year 2 IP administration will not receive the protocol-mandated glucocorticoid regimen until the pause is lifted and Year 2 IP administration takes place; they will remain on their background glucocorticoid regimen until then. If the pause is not lifted within 6 months of the Day 360 (Visit 19), the participant will undergo an unplanned visit for general monitoring on Day 540 \pm 7 days and approximately every 6 months afterwards until the pause is lifted (or more frequently if considered necessary by the investigator), for sites in Israel, see [Appendix 16](#).

At this visit the following tests and assessments will be performed:

- Full physical and neurological examination;
- Vital signs;

- Laboratory blood tests: clinical safety; chemistry and hepatic safety, troponin and CK;
- Functional assessments: NSAA, ROM, and ambulatory status;
- Echocardiogram and ECG.

Once the pause is lifted, participants who have attended Day 360 (Visit 19) more than 90 days before will undergo another unplanned visit to assess eligibility for IP administration. This visit will require the same tests and procedures as the Day 360 (Visit 19) (see [Section 1.3.1](#)). Additionally, sites will enter the weight measured at this unplanned visit into the interactive response technology drug management system to calculate the dose of IP for Year 2 administration and to trigger IP shipment to the site. Participants with an increase or decreased in body weight of more than 5% will have the dose of IP re-calculated

For participants who attended the prior unplanned visit for general monitoring within 90 days of the second unplanned visit to confirm eligibility for Year 2 IP administration, only the following laboratory tests will be performed:

- NAb to AAV9
- INR and hepatitis serology

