8.1.7.1.2. EuroQol 5 Dimensions – Youth Health Questionnaire Proxy Version (EQ-5D-Y Proxy)

The EQ-5D-Y Proxy is a recently developed generic instrument that measures the health status of children. The measure is completed by a caregiver and captures how he or she rates the health of the child. It was adapted from the original EQ-5D questionnaire developed by the EuroQol Group. The EQ-5D-Y Proxy includes five dimensions: mobility (walking around), selfcare (taking care of him/herself), usual activities (doing usual activities), pain/discomfort (having pain or discomfort), and anxiety/depression (feeling worried, sad, or unhappy). Responses record three levels of severity: no problems, some problems, a lot of problems. The EQ-5D-Y Proxy also includes a standard vertical 20 cm visual analogue scale (VAS) for recording current health related quality of life on a scale from 0 to 100, with 0 representing the worst and 100 the best health state he or she can imagine. All items refer to the health state "today".

8.1.7.1.3. Patient Global Impression of Severity – Ambulatory Activities of Daily Living (Caregiver-report; PGIS:CG)

The Patient Global Impression of Severity – Ambulatory Activities of Daily Living (Caregiver-report; PGIS:CG) is a caregiver-completed, 2-item measure of their child's current ability to perform daily activities that require the use of their legs (ie, ambulatory motor function). Motor function is assessed using a 5-point Likert scale with the following options: able to do all, able to do many, able to do some, able to do very little, not able to do any. The PGIS:CG is collected to enable an anchor based method for interpreting changes in the NSAA total score and Modified PODCI scale scores. Details of these analyses will be described in a separate analysis plan.

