Secondary	
Inferential testing of the secondary endpoints will be performed as described in Section 9.1.
 
Baseline is defined as the last non-missing assessment collected prior to Year 1 IP administration.
 
The following endpoints will be analyzed using an analysis of covariance model including model terms for treatment group, Baseline (continuous variable), and Screening age (continuous variable).
 
• Change from Baseline in percent normal mini-dystrophin expression level in biceps brachii muscle biopsies at Day 360 using LC-MS assay.• Change from Baseline in percent of muscle fibers expressing mini-dystrophin in biceps brachii muscle biopsies at Day 360 as assessed by immunofluorescence. 
Change from Baseline at Week 52 in serum CK concentration will be analyzed using a mixed model repeated measures approach and a log transformation. The model fixed effects will be similar to those in the primary endpoint analysis and visits through Week 52 where serum CK concentration is assessed will be included.

Endpoint	Statistical Analysis Methods
	
The below two endpoints will be analyzed using a generalized mixed model assuming a binomial distribution and a logit link. The model terms will include treatment and Screening age (continuous variable).
 
Number of skills gained at Week 52 based on the individual items of the NSAA. For each individual item, a gained skill is defined as a score of 0 at Baseline and a score of 1 or 2 at Week 52.Number of skills either improved or maintained at Week 52 compared to Baseline based on the individual items of the NSAA. For each individual item, an improved or maintained skill is defined as a score of 0 at Baseline and a score of 1 or 2 at Week 52, a score of 1 at Baseline and a score of 2 at Week 52, a score of 1 at Baseline and a score of 1 at Week 52, or a score of 2 at Baseline and a score of 2 at Week 52. 
The following endpoints will be analyzed using a similar mixed model repeated measures approach as used for the primary analysis.
 
Change from Baseline at Week 52 in the 10 meter run/walk velocity;Change from Baseline at Week 52 in the rise from floor velocity;Change from Baseline at Week 52 in the Modified PODCI: Transfer and Basic Mobility Core Scale (Pediatric Parent);Change from Baseline at Week 52 in the Modified PODCI: Sports and Physical Functioning Core Scale (Pediatric Parent).

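### After a Year 1 dosing delay, NSAA is re-measured before dosing but CK and Modified PODCI are not, so three secondary endpoints keep a pre-delay Baseline

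*Protocol*

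**What the plan says.** Protocol Section 5.3.1 covers operational or administrative delays before the first infusion. If the time from Screening to Day 1 "is more than 90 days, participants will undergo an unplanned visit to repeat the following tests and procedures, as applicable". The laboratory line of the list reads "Laboratory tests: clinical safety, chemistry and hepatic safety, cardiac troponin, INR, and hepatitis serology", and the functional line reads "Functional assessments: NSAA, ambulatory status". CK, Modified PODCI, the two global-impression ratings (PGIS:CG and CGIS) and ankle range of motion do not appear.

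CK does not enter through one of the repeated panels. In the Year 1 Schedule of Activities it has its own row, beginning "Biomarker (creatinine kinase", and Table 3 in Appendix 2 lists it under other assessments, apart from the clinical safety and the chemistry and hepatic panels. Its only scheduled pre-dose collection is Visit 2. The same holds for the row "Modified PODCI – Pediatric Parent".

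For the secondary endpoints, Section 9.4.1 states: "Baseline is defined as the last non-missing assessment collected prior to Year 1 IP administration". The NSAA total score has the same rule. Section 3.1 lists change from Baseline at Week 52 in CK and in two PODCI scales among the secondary endpoints.

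**The concern.** The last-value rule combined with a partial repeat list splits the Baseline date within one boy. His NSAA Baseline moves to the unplanned visit, and with it the item scores and the two timed tests recorded during the NSAA (Section 8.1.1). His CK and PODCI Baselines stay where they were before the delay.

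Two things are at stake for those three endpoints. First, a quantity labelled as a Week 52 change covers a longer and variable period in delayed boys. Section 4.2.2 describes motor function as improving through age 5 and holding level through age 7, so extra time before dosing is not necessarily neutral in boys aged 4 to 7. Second, an older Baseline is likely to be a weaker covariate in the model. An analysis plan cannot repair either problem, because the later pre-dose value would never have been collected.

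**Working it through.** **Who is affected.** Only boys who had completed Visit 2 before the delay and whose time from Screening to Day 1 exceeds 90 days. A boy not yet at Visit 2 has CK and PODCI taken later, at Visit 2 itself.

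**Which endpoints.** Section 3.1 has nine secondary endpoints.
- Refreshed with the NSAA: 10-meter velocity, rise-from-floor velocity, skills gained, skills improved or maintained (4).
- Left at the pre-delay value: CK, PODCI Transfer and Basic Mobility, PODCI Sports and Physical Functioning (3).
- Also not repeated: the two biopsy endpoints. They come from an invasive procedure in a subset, and no repeat is suggested here.

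**Length of the change interval.** The Schedule of Activities places Visit 2 16 to 48 days before Day 1.
- Usual span: 52 + 16/7 = 54.3 weeks to 52 + 48/7 = 58.9 weeks.
- With a delay of *d* weeks after Visit 2: 54.3 + *d* to 58.9 + *d*.

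The protocol gives no length for a Year 1 delay, so *d* is an assumption:

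| Assumed delay *d* | Span (weeks) | Ratio to usual span |
|---|---|---|
| 4 weeks | 58.3 to 62.9 | 1.07 (both ends) |
| 13 weeks | 67.3 to 71.9 | 1.24 to 1.22 |
| 26 weeks | 80.3 to 84.9 | 1.48 to 1.44 |

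The comparator is the usual 54 to 59 weeks, not 52, because some lead time is built into every boy's Baseline.

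**Precision, as an illustration.** Let a share *f* of participants be delayed, and let the correlation between Baseline and Week 52 fall from r0 to r1 in those boys. Relative residual variance = [(1 − f)(1 − r0²) + f(1 − r1²)] / (1 − r0²). None of *f*, r0 or r1 is in the protocol.
- r0 = 0.7, r1 = 0.5: *f* = 10% gives (0.9 × 0.51 + 0.1 × 0.75)/0.51 = 1.047; *f* = 30% gives 1.141.
- r0 = 0.8, r1 = 0.6: *f* = 10% gives (0.9 × 0.36 + 0.1 × 0.64)/0.36 = 1.078; *f* = 30% gives 1.233.

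The standard error rises by the square root of these: about 2% (√1.047 = 1.023) to 11% (√1.233 = 1.110).

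**The plan's own figure.** The protocol states no number for this issue. Its 98% power in Section 9.2 concerns the NSAA. A fixed-sample check with 64 and 32 evaluable boys, difference 3.0 and SD 3.5 gives 3.0/(3.5 × √(1/64 + 1/32)) = 3.96, hence power Φ(3.96 − 1.96) = 97.7%. That agrees with the plan, and nothing here changes it.

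**Comparison with Year 2.** Section 5.3.2 describes two visits. The monitoring visit lists "Laboratory blood tests: clinical safety; chemistry and hepatic safety, troponin and CK". The later visit to re-check eligibility repeats the Visit 19 procedures, which include CK and PODCI, unless a monitoring visit took place within the preceding 90 days. On its main path, then, the protocol refreshes these measures before a delayed Year 2 infusion but not before a delayed Year 1 infusion.

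**The case against.** The strongest reply is that the Year 1 visit does what it is for. Sections 5.3, 5.3.1 and 5.6 present it as re-confirming eligibility. NSAA score and ambulation are eligibility criteria; CK and PODCI are not. This explains the omission and means the protocol does not contradict itself. It does not shorten the change interval, because Section 9.4.1 turns whatever was measured at that visit into the Baseline.

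The Year 2 comparison also has limits. The monitoring list quoted above is for boys already dosed, in whom CK is a safety marker (Section 2.3.2), and it omits PODCI. When that visit falls within 90 days of the re-eligibility visit, only the AAV9 antibody test, INR and hepatitis serology are added. The Year 2 path is therefore a precedent for the fix and does not prove an error.

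A reader might infer that the protocol foresees Year 1 delays beyond 6 months. The 6-month rule belongs to the Year 2 pause. The Year 1 trigger is more than 90 days from Screening, and an overrun could be a few days.

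A reader might also infer that interpretation of NSAA change is compromised because the anchors stay at Visit 2. The protocol does say: "The PGIS:CG is collected to enable an anchor based method for interpreting changes in the NSAA total score and Modified PODCI scale scores". But Sections 8.1.7.1.3 and 8.1.7.3.1 refer that analysis to a separate plan, which could pair the Visit 2 NSAA with the Visit 2 anchors. Section 8.1.7.3.1 also ties CGIS to the evaluator who completes the NSAA at each visit, so some sites may collect it anyway. No anchor error is established.

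**Conclusion.** The point holds in a limited form. For boys past Visit 2 whose Year 1 dosing is delayed, CK and both PODCI scales keep a pre-delay Baseline while NSAA and its four derived secondary endpoints are refreshed. The three affected changes span the delay plus the usual 54 to 59 weeks. On the assumption of a 26-week delay that is about 80 to 85 weeks, or 1.44 to 1.48 times usual; shorter delays do proportionately less.

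The consequence is modest. CK and PODCI lie outside the alpha-controlled sequence in Section 9.1, and the primary endpoint and the four endpoints in that sequence use the refreshed NSAA. The delay precedes dosing in a randomised, blinded comparison, so it should cost precision and interpretability without favouring an arm. The 5% to 23% rise in residual variance is illustrative only, since the number of delayed boys and the correlations are not given. This is a cheap improvement and does not threaten the trial's main conclusion.

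**What to change.** In Section 5.3.1, for participants who have already completed Visit 2, add two items to the repeated assessments:
- CK, drawn before the functional tests as the Schedule of Activities asks elsewhere, and within the blood volume limits in Section 8.
- Modified PODCI (Pediatric Parent).

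This matches what the Year 2 re-eligibility visit generally does. Blinding is no obstacle, because Section 6.3.3 withholds CK results only after Year 1 dosing.

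PGIS:CG and CGIS may be added at the same visit so that same-date anchors exist. Ankle range of motion supports an exploratory endpoint and is optional. For boys already dosed after a delay the missing value cannot be recovered; reporting the interval from Baseline to Day 1 for CK and PODCI would let readers judge its effect.

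The cost is an amendment to one list, plus one extra analyte and a short caregiver questionnaire for the delayed boys, at a visit and blood draw that are already required.

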5.3.2. Year 2 IP Administration Eligibility

If, due to operational or administrative reasons (eg, enrollment pause due to regulatory or safety review, operational issues causing significant delays), a participant's Year 2 IP administration must be delayed, the Day 390 (Visit 20) and also subsequent visits will be delayed for that participant until the pause is lifted. Participants with delayed Year 2 IP administration will not receive the protocol-mandated glucocorticoid regimen until the pause is lifted and Year 2 IP administration takes place; they will remain on their background glucocorticoid regimen until then. If the pause is not lifted within 6 months of the Day 360 (Visit 19), the participant will undergo an unplanned visit for general monitoring on Day 540 \pm 7 days and approximately every 6 months afterwards until the pause is lifted (or more frequently if considered necessary by the investigator), for sites in Israel, see [Appendix 16](#).

At this visit the following tests and assessments will be performed:

- Full physical and neurological examination;
- Vital signs;

- Laboratory blood tests: clinical safety; chemistry and hepatic safety, troponin and CK;
- Functional assessments: NSAA, ROM, and ambulatory status;
- Echocardiogram and ECG.

Once the pause is lifted, participants who have attended Day 360 (Visit 19) more than 90 days before will undergo another unplanned visit to assess eligibility for IP administration. This visit will require the same tests and procedures as the Day 360 (Visit 19) (see [Section 1.3.1](#)). Additionally, sites will enter the weight measured at this unplanned visit into the interactive response technology drug management system to calculate the dose of IP for Year 2 administration and to trigger IP shipment to the site. Participants with an increase or decreased in body weight of more than 5% will have the dose of IP re-calculated

For participants who attended the prior unplanned visit for general monitoring within 90 days of the second unplanned visit to confirm eligibility for Year 2 IP administration, only the following laboratory tests will be performed:

- NAb to AAV9
- INR and hepatitis serology

For participants confirmed to be eligible for Year 2 IP administration by the unblinded medical monitor (see [Section 7.1](#)), Day 390 (Visit 20) should take place within 30 days of the unplanned visit. At this visit the investigator will review the additional Year 2 IP administration eligibility criteria (see [Section 7.1](#)) and confirm if the participant can receive IP. After Year 2 IP administration has taken place, participants will continue to follow the regular protocol [Schedule of Activities](#); the days in study will be counted starting on the day of Year 2 IP administration.

